9.6 SAMPLE SIZE

For the pivotal study, a sufficient number of healthy adults will be screened with volunteer's consent and 60 subjects will be randomized under fasting conditions.

When possible, subjects will be enrolled in three echelons for all the planned number of subjects. If the capability/capacity of the clinical study facility is limited during the enrollment, the planned subjects may be split into 3 or more echelons with minimal 18 subjects in each echelon. **If the minimal subject number per echelon fails to meet the requirement, it is acceptable to split more echelons to achieve the designated sample size, as specified in the protocol.** In the circumstance the subjects are enrolled in split groups, statistical analysis will NOT be carried out before all the planned subjects have completed the study. Details for considerations of potential group effects will be stipulated separately in the statistical analysis plan.

9.7 DROPOUT AND WITHDRAWAL/TERMINATION

After administration, dropouts should not be replaced for any reason.

The following circumstances may lead to discontinuation of the study by an individual subject who will then be recorded as a drop-out:

- Withdrawal at any time for any reason
- AE necessitating withdrawal from the study
- Circumstances in which the health of the subject would be endangered upon continued participation in the study
- Protocol violation which could jeopardize the conduct of the study as judged by principal investigator
- For female with positive pregnancy test prior dosing
- Incorrect use of investigational product while dosing (e.g. any leak of investigational product from mouth while dosing)

Removal of a subject from the study will only be permitted prior to commencement of bioanalysis. If a subject's participation is terminated prematurely, the cause for the early termination date and time of the termination will be documented on the source documents and in the final study report. Withdrawn and dismissed subjects are not required to adhere to the study specific procedures (e.g. food and fluid restrictions, sample collections). If withdrawn or dismissed after drug administration, these subjects will be asked to adhere to the study restrictions in regards to the safety, prescription medication, over-the-counter medication, dietary and/or herbal supplements for the expected

duration of the restrictions relevant to the study period which the subject withdraws or is dismissed from (that period will be the subject's last study period). Subjects will be asked to adhere to the requirements of not becoming pregnant and using a medically acceptable method of contraception for 30 days after discontinuation in the study (if applicable).

If a subject withdraws or is dismissed from the study, a post-study physical examination and post-study testing will be completed, where possible.

10. DRUG PRODUCTS

10.1 DRUG INFORMATION

Treatment Code	T	R
Drug Name:	Albuterol Sulfate inhalation aerosol 108mcg per actuation (equivalent to 90mcg of Albuterol)	Proair HFA(albuterol sulfate) Inhalation Aerosol 90 mcg per actuation
Active ingredient:	Albuterol sulfate	Albuterol sulfate
Strength:	eq. to albuterol 90mcg/puff	eq. to albuterol 90mcg/puff
Dosage Form:	MDI	MDI
Manufactured by:	Intech Biopharm Ltd.	IVAX Pharmaceuticals Ireland Waterford, Ireland
Dose:	Single dosing, 180mcg (2 puffs)	Single dosing, 180mcg (2 puffs)
Mode of administration:	Inhalation	Inhalation
Batch Number	ALMB040	DAE50A

10.2 LABELING, MAINTENANCE, AND RETENTION OF STUDY DRUGS

The Sponsor will supply a sufficient quantity of the study formulation(s) to allow completion of this study. Records will be made of receipt and dispensing of study drugs supplied and will be maintained by the Pharmacy staff. It is the responsibility of the Sponsor to ensure that all drug supplies provided for the study are manufactured under current Good Manufacturing Practices and

are suitable for human use.

The pharmacist will randomly select the boxes or bottles or containers to be used in the study. An inventory record of the drugs received and dispensed will be maintained by the Pharmacy staff. Each investigational study drug will be tagged with a statement indicating that the drug is an investigational drug to be used only by a Qualified Investigator as well as, Drug Name, Protocol Number, Strength, Sponsor's Name, the recommended storage conditions for the drug, Expiry Date (when available) and Lot/Batch Number. Study drugs will be locked in a temperature controlled room with restricted access. The study drugs will be prepared by pharmacy staff into individual unit-dose containers. Each unit-dose container will contain the Protocol Number, Period Number, Subject Number, Drug Name, Strength and Treatment Code.

11. STUDY PROCEDURES

Efficacy and Safety Measurements and Flow Chart

Clinical Study Protocol

Procedure/Activity	Screening	Each Period Check-in	Period 1 and 2	Post study examinations
ICF	X			
Urine tests for drugs of abuse	X	X		
Breath alcohol test	X	X		
Medical History	X			
Physical Exam	X			X
Chest X-ray ^a	X			
ECG ^a	X			
BMI	X			
Vital sign ^b (BP, PR and Temperature)	X		X	
AE Reporting (including PTE) ^c	X	X	X	X
Laboratory tests ^γ				
Hematology	X			X
Biochemistry	X			X
Urinalysis	X			X
Serology	X			
Pregnancy test ^δ	X	X		X
Inclusion/Exclusion Assessment	X			
Restrictions Compliance Check		X	X	
Drug administration			X	
PK Sampling			X	
Meals			X	

a The results of ECG and chest X-Ray within previous 30 days will be accepted for evaluation.

β Details refer to Section 11. Dosing Procedures and Sampling Time Schedule.

γ Details refer to Section 9.2.

δ For females subjects, serum hCG will be performed only at screening. Urine hCG will be performed at check in of each period and post examination.

ε This study will collect pretreatment event (PTE) and adverse event (AE) after subjects provide written consent in the ICF. Only AE occur after first dosing will be analyzed for safety assessment.

The following section describes the scheduled intervals for this study, whereas the planned time

Clinical Study Protocol

listed herein is to serve as examples only. The actual time executed for each individual subject will be advanced or postponed for several hours.

Dosing Procedures and Sampling Time Schedule^a

Day	Time	Events	Corresponding time after dosing		Number of Sampling ^c	Vital Signs Measuring ^c
			Hours	hh:mm		
-1	≤21:00	Subjects Check-in	-		-	
	21:30	Start of fasting	-		-	
1	07:00		Pre-dose ^γ		1	δ
	07:30	Dosing ^β	0	+00:00	-	
	07:32		0.033	+00:02	2	
	07:35		0.083	+00:05	3	
	07:40		0.167	+00:10	4	
	07:45		0.25	+00:15	5	
	08:50		0.333	+00:20	6	
	08:00		0.5	+00:30	7	δ
	08:15		0.75	+00:45	8	
	08:30		1.0	+01:00	9	
	08:45		1.25	+01:15	10	
	09:00		1.5	+01:30	11	
	09:15		1.75	+01:45	12	
	09:30		2.0	+02:00	13	
2	09:45		2.25	+02:15	14	
	10:00		2.5	+02:30	15	
	10:30		3.0	+03:00	16	
	11:30	End of fasting and start of lunch	4.0	+04:00	17	
	13:30		6.0	+06:00	18	
	15:30		8.0	+08:00	19	
	17:30	Dinner	10	+10:00	-	
	19:30		12.0	+12:00	20	
	23:30		16.0	+16:00	21	δ
	07:30		24.0	+24:00	22	δ

^a Time schedule listed herein is to serve as examples. For each individual subject, the execution of subsequent sampling

time will be corresponding to the actual dosing time in relation to the ascending order of random number.

β Subjects will be administered an orally inhaled dose of 2 puffs (eq. to albuterol 180 mcg) under fasting conditions.

Both start time and end time of inhalation will be recorded.

γ Pre-dose sample will be collected within 60 minutes before dosing and shown as 0 hour sample in bioanalytical and statistical analysis report.

δ Vital signs: BP, PR and body temperature.

ε The suggested time windows for sampling time are listed as follows (Sampling deviation within time window will not apply to protocol deviation):

Sample No.	No. 2-9	No. 10-21	No. 22
Time window	+2 minutes	+5 minutes	+60 minutes

ζ Pre-dose vital signs will be measured within 2 hours of administration. On dosing day, the acceptable window of vital sign is \pm 30 minutes. The non-administration day acceptable window will be measured within \pm 60 minutes at a predetermined time. (Measurement of vital sign within time window or vital sign rechecked time exceeding the time window will not be considered as a protocol deviation.)

11.1 STUDY PERIOD CHECK-IN PROCEDURES

At check-in for each study period, subjects will be questioned about whether they have complied with the study restrictions.

If drug therapy other than that specified in the protocol is used, a decision to continue or discontinue the subject's participation will be made by the Principal Investigator/Sub-Investigator and/or by the PPC Pharmacokineticist and/or by the Sponsor.

Urine tests for drugs of abuse and a breath alcohol test will be performed on all subjects at each study period check-in. In addition, urine hCG testing will be performed on all female subjects at each study period check-in.

Clinical staff reserves the right to conduct random testing (urine drugs of abuse, urine hCG [females only], or breath alcohol) on any subject at any time during the study to ensure subject compliance and/or safety.

Any subjects with a positive test for urine drugs of abuse, or breathe alcohol or urine hCG (females only) will be withdrawn from the study immediately.

11.2 FOOD AND FLUID INTAKE

The day before the study (Day -1), subjects must arrive at clinical facility by 21:00. Subjects will

remain fasted at least 10 hours before dosing and a minimum of 4 hours thereafter. Subjects will be given standardized meals and caffeine/methylxanthine-free beverages at scheduled times. Meals will be served at approximately 4 and 10 hours after dosing on Day 1, and any other food is prohibited. Meals and beverages during confinement will be identical (if feasible) for each study period.

Water will be prohibited 1 hour prior to dosing and restricted until 2 hour after inhalation. No fluids other than water and those served for administration/with meals will be permitted during the confinement.

11.3 VITAL SIGNS MEASUREMENTS

In the interest of subject safety, staff will monitor vital signs (BP, PR, and temperature) at pre-dose and at 0.5, 16 and 24 hours post-dose in each study period.

Pre-Dose and Post-Dose:

All subjects with vital signs outside of acceptable range of systolic blood pressure between 90-139 mmHg, inclusive, diastolic blood pressure between 50-90 mmHg, inclusive, and pulse rate between 50-100 bpm, inclusive, will have their vital signs repeated up to two times. If vital signs are still outside of acceptable range Principal Investigator/Sub-Investigator will determine appropriate course of action.

Additional vital signs measurements will be taken if deemed necessary by the Principal Investigator/Sub-Investigator. Blood draws will take precedence over vital signs measurements and other scheduled activities, should a timing conflict arise unless deemed necessary by the Principal Investigator/Sub-Investigator.

11.4 CHEST X-RAY AND ECG MONITORING

Chest X-ray and ECG measurements will be performed at screening. For each period, Chest X-ray **and** ECG measurements are not required unless deemed necessary by the Principal Investigator/Sub-Investigator.

11.5 ADDITIONAL TESTING

Additional tests are not required during the study unless deemed necessary by the Principal Investigator/Sub-Investigator.

11.6 DOSING

Subjects will take their assigned formulation, designated by the randomization scheme, after at least a 10-hour fasting period at their scheduled time-point.

Two puffs (eq. to albuterol 180 mcg) of test product and reference product will be inhaled per orally. The investigational product will be inhaled with adequate time intervals between subjects to ensure correct blood sampling.

11.7 PHYSICAL ACTIVITY

Subjects will stay awake and remain seated in an upright position for the first 4 hours following drug administration, and allowed to rise under supervision only for brief periods of time, in order to comply with study-related activities and to use the washroom. After the first 4 hours they will be allowed to ambulate freely within the clinic. However, if a medical event (i.e. AE) occurs, subjects may be placed in an appropriate position at any time. Subjects will be required to abstain from strenuous activities for the duration of the study period(s).

11.8 BLOOD SAMPLING SCHEDULE, SAMPLE COLLECTION, PROCESSING AND STORAGE

Samples will be collected through an indwelling cannula (if possible) placed in a vein. The pre-dose samples will be collected prior to drug dosing. Intravenous indwelling cannula would be kept in place up to 24 hours post-dose by injecting adequate amount but not more than 0.5 ml of normal saline solution during the collection of multiple samples. In such case, the blood sample would be collected after discarding the first 0.5 ml of blood from the tubing. Blood may also be withdrawn by a fresh clean venipuncture either by using sterile syringe and needle or disposable sterilized needle and vacutainer if the cannula is blocked.

If the blood sample collection time coincides with the other study events like vitals, subject well-being questionnaire and meal, the sequence of the events would be followed as: blood sample collection / vitals > subject well-being questionnaire > meal / water.

During the study, blood sample are collected from vein. Subject may suffer the common AE with donating blood, including vasovagal syncope (including temporary weakness, dizzy and nausea) and ecchymoma.

Number of Samples	For each subject, the total number of blood draws will be 44 (22 samplings x 2 periods).
Total Volume of Blood (for all periods, including approximately 20 ml for pre-, and post-study procedures)	7 ml of venous blood samples will be collected according to time-point schedule. The total volume of blood withdrawn will be approximately 328 ml, (Up to 10 ml for screening, approximately 308 ml for the two periods and up to 10 ml for post study laboratory test at the end of last period).
Blood Sampling Time Points	0-hour (Pre-dose), and at 2, 5, 10, 15, 20, 30, 45 minutes, and 1, 1.25, 1.5, 1.75, 2, 2.25, 2.5, 3, 4, 6, 8, 12, 16 and 24 hours post-dose in each study period.

Type of specimens: plasma

Each blood sample will be collected into a pre-labeled tube containing an applicable anti-coagulant (e.g., heparin sodium or EDTA, depending on the analytic methods to be used). The label includes the trial number, random number, sampling time point, and study period number. The samples collected at each time point will be centrifuged (1900g and 4°C for 10 minutes or other applicable conditions) to separate the plasma from the whole blood within 30 minutes after drawing the blood samples from the subjects.

The separated plasma will be aliquoted into two batches (if feasible), transferred to appropriately labeled tubes, and then stored in a freezer with a temperature of -20°C or lower at the clinical facility. After the collection and centrifugation procedures, the samples will be maintained in an ice-bath container until stored in the freezer at the clinical facility.

The time between the blood centrifugation and the freezer storage should, in general, not exceed 1 hour. However, exception can be made to allow the above processing time up to 2 hours if the prolonged time period will not interfere with the stability of the analyte(s).

The first of the plasma samples will be packaged with dry ice and delivered from the clinical facility to bioanalytical lab with temperature recording. This first batch will be stored in a freezer with a temperature of -20°C or lower at the bioanalytical lab until further analysis; the other batch as

back-up will be stored in the freezer of clinical facility and will be delivered separately thereafter if required.

11.9 HEALTHY STATUS MONITORING

Health monitoring will be conducted throughout the study or as needed. AE will be reported and monitored after the first dose of the study drug.

11.10 POST-STUDY TESTS

An exit physical examination will be conducted upon completion of the study or after withdrawal/dismissal of a subject from the study, where possible.

Within 7 days after completion of the clinical part, a clinical laboratory tests (hematology, biochemistry and urinalysis), as per section 9.2 Clinical Laboratory Assessment, will be performed in order to determine possible changes in the subject's state of health. Study personnel should contact those subjects who do not come back for the post study examinations within a week, and then a 3-day grace period will be given. The subjects will be considered as lost to follow-up after the grace period, and all communication should be recorded. In addition, urine hCG testing will be performed on all female subjects at post-study.

11.11 SAMPLE SHIPMENT

The samples from all subjects will be delivered to the analytical facility packed on dry ice. All shipments will be accompanied by an inventory list and delivered to the analytical laboratory. Clinical personnel will notify the analytical laboratory prior to shipment by phone, fax or e-mail.

12. ADVERSE EVENT

PPC has established SOP in conformity with regulatory requirements to ensure the timely, accurate, and complete reporting of safety information. This study will collect PTE and AE after subjects provide written consent in the ICF. Only AE occur after first dosing will be analyzed for safety assessment.

12.1 ADVERSE EVENT RECORDING AND FOLLOW-UP

Subjects will be instructed to inform clinical personnel of any untoward medical symptoms and/or events that may arise during the course of the study.

Prior to the subsequent study period, subjects will be questioned concerning symptoms that may have occurred after the previous administration of the study drug(s). The incidence, severity and duration of all AE will be recorded according to the following scale:

Mild	AE resulting in discomfort, but not sufficient to cause interference in normal daily activities.
Moderate	AE resulting in discomfort that is sufficient to cause interference in daily activities.
Severe	AE resulting in discomfort causing an inability to carry out normal daily activities.

AE monitoring and reporting will be followed up until resolution or stabilization at an acceptable level and thereafter the Principal Investigator or Sub-investigator will decide the course of action.

12.2 ASSESSING RELATIONSHIP TO STUDY DRUG

The Principal Investigator/Sub-Investigator will assess the relationship of all adverse reactions to the drug, using the following scale:

Certain: A clinical event, including laboratory test abnormality, occurring in a plausible time relationship to drug administration, and which cannot be explained by concurrent disease or other drugs or chemical. The response to withdrawal of the drug (de-challenge) should be clinically plausible. The event must be definitive pharmacological or phenomenological, using a satisfactory re-challenge procedure if necessary.

Probable/ likely: A clinical event, including laboratory test abnormality, with a reasonable time sequence to administration of the drug, unlikely to be attributed to concurrent disease or other drugs or chemicals, and which follows an clinically reasonable response to an withdrawal (de-challenge). Re-challenge information is not required to fulfill this definition

Possible: A clinical event, including laboratory test abnormality, with a reasonable time sequence to administration of the drug, but which could also be explained by concurrent disease or other drugs or chemicals. Information on drug withdrawal may be lacking or unclear.

Unlikely: A clinical event, including laboratory test abnormality, with a temporal relationship to drug administration which makes a causal relationship improbable, and in which other drugs, chemicals or underlying disease provides plausible explanation.

Unrelated: A report suggesting an adverse reaction which cannot be judged because information is insufficient or contradictory, and which cannot be supplemented or verified.

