16.2 QUALITY OF DATA

All source documents and laboratory reports will be Quality Control reviewed to ensure accuracy and completeness. AE will be reviewed and assessed for severity and causality by the Principal Investigator/Sub-Investigator. Specific processes of the study, its source documentation and any reports (if applicable) will be audited by the Quality Assurance unit of PPC.

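### Protocol 12.2 puts the label *Unrelated* on the definition of an event that cannot be assessed, so label and definition contradict each other and a truly unrelated event has no written definition

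*Protocol*

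**What the plan says.** Protocol 12.2 introduces the scale with "The Principal Investigator/Sub-Investigator will assess the relationship of all adverse reactions to the drug, using the following scale". The levels are *Certain*, *Probable/likely*, *Possible*, *Unlikely* and *Unrelated*.

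The last level is worded "Unrelated: A report suggesting an adverse reaction which cannot be judged because information is insufficient or contradictory", and the sentence ends "and which cannot be supplemented or verified". There is no separate level for an event that cannot be assessed.

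The neighbouring level, *Unlikely*, needs timing that makes a causal link improbable and also a case "in which other drugs, chemicals or underlying disease provides plausible explanation".

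Protocol 16.2 confirms that the scale will be used: "AE will be reviewed and assessed for severity and causality by the Principal Investigator/Sub-Investigator". Protocol 12 adds that "PPC has established SOP in conformity with regulatory requirements to ensure the timely, accurate, and complete reporting of safety information", but that procedure is not among the documents.

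**The concern.** A causality code should mean one thing to the person who assigns it and to the person who reads it. Here the label says that the drug was not the cause, while the text beneath it describes a report that suggests a reaction and cannot be resolved. Two assessors could give the same code opposite meanings, and a reader of the data could not tell which was meant.

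What is at stake is the causality recorded for individual AEs: *could not be judged* may end up reading as *not caused by the drug*. The bioequivalence conclusion is not at stake.

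**Working it through.** No arithmetic applies, because the documents give no AE rate and no share of events that cannot be assessed. The check is a reading of the five levels side by side, then of every place where the code could be used.

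**Step 1. Label against definition (Protocol 12.2).**

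| Label | What the definition describes | Agree? |
|---|---|---|
| *Certain* | plausible timing, no other explanation, supported by de-challenge | yes |
| *Probable/likely* | reasonable timing, other causes unlikely, reasonable de-challenge | yes |
| *Possible* | reasonable timing, "but which could also be explained by concurrent disease or other drugs or chemicals" | yes |
| *Unlikely* | timing makes causality improbable, and another explanation exists | yes |
| *Unrelated* | no judgement possible, and the information cannot be completed | no |

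Four levels grade causal likelihood. The fifth describes the absence of a judgement but carries the label for the absence of a relationship. So 1 of 5 labels contradicts its definition.

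**Step 2. Is this current text, and is it corrected elsewhere?** The revision table in Protocol 1.1 shows that version 2.0 affected only section 9.6, so 12.2 is current. The sentence is complete, with no sign of redaction. No other visible section of the Protocol or SAP defines *unrelated* or *unassessable*.

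**Step 3. Run three kinds of event through the scale.**

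| Event | If the definition is followed | If the label is followed |
|---|---|---|
| Suspected reaction, information insufficient and not recoverable | coded *Unrelated* | no code |
| Event clearly due to another cause, with timing that fits the drug | no matching definition | coded *Unrelated*, on plain meaning only |
| Fully documented event, timing makes a drug effect improbable, no other cause found | no matching definition: *Unlikely* also needs another explanation, and the information is not insufficient | *Unrelated* on plain meaning, or *Unlikely* by stretching it |

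Each reading leaves a gap, and neither supplies a written definition of a truly unrelated event.

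**Step 4. Where could the code have an effect?**
- Protocol 12.3: serious AEs are reported to the sponsor regardless of causality. Notification of the IRB and regulators applies where applicable, with no criteria given, so whether it depends on causality is unknown.
- Protocol 12.1: follow-up to resolution or stabilisation does not depend on causality.
- Protocol 9.7 and 14.1: withdrawal for an AE, and removal of such subjects from the pharmacokinetic data set, do not depend on causality.
- SAP 8.6 and SAP 12 (Format of listing): safety output is listings. Only the title of Listing 16.12 is shown, and no grouping into related and not related is planned.

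No visible rule acts on the code. The contradiction reaches a report only if causality is shown in an AE listing or elsewhere in the study report.

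**The case against.** The strongest reply is that investigators know what *unrelated* means and will use it that way, so nothing will be miscoded. That is possible, and the documents do not exclude it. It does not remove the defect: the investigator would be departing from the written definition, and an event that cannot be assessed would have no code.

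A second reply is that the situation will be rare. Subjects are healthy, receive single doses, stay in the clinic until at least 24 hours after dosing, and have an investigator present from about 30 minutes before dosing until 4 hours after it (Protocol Synopsis and 8.2). They are questioned about symptoms before the next period (12.1), and symptoms are reviewed before any further dosing (12.3). Information that can never be recovered should therefore be uncommon. This stands, and it limits the size of the point.

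A third reply is that the safety procedure cited in Protocol 12 may define the codes properly. It may, but an unseen procedure does not make the Protocol consistent with itself.

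Two further inferences are tempting. The four other definitions name only disease, other drugs or chemicals as alternative causes, although Protocol 11.8 warns "Subject may suffer the common AE with donating blood, including vasovagal syncope (including temporary weakness, dizzy and nausea) and ecchymoma" and schedules 44 draws per subject (22 samplings × 2 periods). A reader might infer that blood-sampling events will be miscoded. The documents do not show that: 12.2 concerns relationship to the drug, and leaving procedures off the list contradicts nothing. A reader might also infer from the words *adverse reactions* in 12.2 that some AEs escape assessment. Protocol 16.2 provides for the assessment of AEs, so this is loose wording and not a gap.

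**Conclusion.** The contradiction in Protocol 12.2 is real and visible on the page. Its size is minor. It concerns one label out of five and affects only the causality coding of AEs. The number of affected events is unknown and may be zero.

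A reader might infer that unassessable reactions will certainly be recorded as not drug-related, or that safety reporting is compromised. The documents support neither. They show that label and definition disagree, but not which one investigators will follow. Reporting of serious AEs to the sponsor does not use the code, and no claim can be made about IRB or regulatory notification.

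The conclusion rests on two assumptions: that *Unrelated* is read in its plain sense, since no rule for grouping the levels is given, and that nothing outside the two documents overrides 12.2.

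**What to change.** In Protocol 12.2:
1. Relabel the existing text *Unassessable*.
2. Add a separate *Unrelated* level: no reasonable possibility of a causal relationship to the study drug, either because the timing is incompatible with a drug effect (whether or not another cause is identified), or because another cause, including a study procedure, clearly explains the event.
3. State that *Unlikely* applies when a causal relationship is improbable but not excluded, whether or not another cause has been identified. The two levels then do not overlap, and a documented event with improbable timing and no known cause has a place.

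Wherever causality is listed, show unassessable events under their own code and do not pool them with *Unrelated*. Align the code list in the case report form and electronic data capture (Protocol 16.1) and check the safety procedure cited in Protocol 12. Re-review any AE already coded *Unrelated* against the separate definitions.

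Naming study procedures in the other definitions, and changing *adverse reactions* to *adverse events* in the opening sentence, are optional clarifications.

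The cost is one extra causality code and a minor amendment. Under Protocol 15.4 this needs approval by the Principal Investigator and the Sponsor, and submission to the IRB, which applies even to clarifications. No visit or study procedure is added.
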